#### **5.2.15 Simpson-Angus Scale (SAS)**

The SAS is a measure of extrapyramidal side effects (EPS) and consists of a list of 10 symptoms of Parkinsonism (gait, arm dropping, shoulder shaking, elbow rigidity, wrist rigidity, leg pendulousness, head dropping, glabella tap, tremor, and salivation). Each item will be rated on a 5-point scale, with a score of 0 representing absence of symptoms, and a score of 4 representing a severe condition. The SAS total score is the sum of the scores for all 10 items.

#### **5.2.16 Abnormal Involuntary Movement Scale (AIMS)**

The AIMS assessment consists of 10 items describing symptoms of dyskinesia. Each item will be rated on a 5-point scale, with a score of 0 representing absence of symptoms (for item 10, no awareness), and a score of 4 indicating a severe condition (for item 10, awareness, severe distress). The AIMS movement rating score is defined as the sum of items 1 through 7 (i.e., items 1 through 4, facial and oral movements; items 5 and 6, extremity movements; and item 7, trunk movements).

#### **5.2.17 Unscheduled Visits**

Only values collected at scheduled assessments values will be tabulated, unless otherwise stated. All repeat/unscheduled assessments will be included in all listings in the relevant appendices to the Clinical Study Report (CSR).

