7.2.2 Visit 2 (Baseline, Study Day 1)

At this visit, the following assessments will be performed and recorded in the patient's source documentation/medical record and in the eCRF:

- Review of inclusion and exclusion criteria
- Recording of concomitant medications (e.g., prescription and nonprescription medications)
- Targeted physical examination (if applicable)
- Body weight, BMI (derived programmatically from body weight and height measurements), and waist circumference
- Vital signs
- Resting 12-lead ECG (triplicate, further information in Section 8.2.3)
- Collection of blood and urine samples for clinical laboratory tests. Additional information is presented in the footnotes to the SoA (Table)
- Urine pregnancy test for all females of childbearing potential
- Assessment and recording of AEs
- PANSS- patients with improvement of ≥20% in total PANSS score between the Screening and Baseline assessments will be excluded from study participation. PCRS must be administered before PANSS
- CGI-S
- C-SSRS
- Randomization
- Pre-dose PK blood sample will be collected
- Study drug administration

Confidential Page 59 of 102

- PK sample collection for the first 60 patients randomized regardless of cohort at the following timepoints after the morning dose: 15 minutes, 30 minutes, 1, 2, 3, 4, 8, and 24 hours
- AIMS, 3 to 6 hours post-dose
- BARS, 3 to 6 hours post-dose
- SAS, 3 to 6 hours post-dose
- Cogstate test

7.2.3 Study Days 2 Through 7

On Days 2, 3, 4, 5, 6, and 7 each patient may receive the QD administration of study treatment. No other assessments are scheduled; however, AEs observed or reported, and concomitant medications may be recorded. If any assessments are required in order to evaluate an AE, an unscheduled visit may be conducted, at the discretion of the PI.

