8.2.4 Clinical Laboratory Tests

The following clinical laboratory tests (samples are to be taken after an overnight fast of at least 8 hours) are to be performed as indicated in the SoA (Table):

- *Hematology:* hemoglobin, hematocrit, red blood cell (RBC) count, white blood cell (WBC) count (with differential), and platelet count
- *Coagulation:* PT, aPTT, and INR
- *Chemistry:* albumin, albumin/globulin ratio, ALT, alkaline phosphatase, AST, bilirubin-direct, bilirubin-indirect, bilirubin-total, blood urea nitrogen, blood urea nitrogen/creatinine ratio, calcium, chloride, creatine kinase, creatinine, gamma-glutamyl transpeptidase, globulin, glucose, HbA1c, lactate dehydrogenase, phosphate, potassium, prolactin, sodium, total cholesterol, triglycerides, HDL, LDL, and uric acid
- *Urinalysis:* pH of freshly voided specimen, specific gravity, protein, glucose, ketones, blood, and microscopic examination of the sediment

Confidential Page 68 of 102

- *Pregnancy tests*: urine or serum pregnancy tests, only required for female patients of childbearing potential (e.g., not postmenopausal or surgically sterile [hysterectomy, bilateral oophorectomy, and/or bilateral salpingectomy])
- Other: urine drug screen/blood alcohol test and TSH
- ACTH and cortisol

Laboratory samples will be analyzed by a central laboratory to ensure consistent interpretation of results. Additional details on the processing and shipment of specimens are provided in the Laboratory Manual. In the event of an unexplained clinically noteworthy abnormal laboratory test value, the test should be repeated immediately and followed up until it has returned to the normal range and/or an adequate explanation of the abnormality is found.

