### 5.2.2 Baseline

Baseline is defined as the last non-missing value (either scheduled, unscheduled, or repeat) before the patient receives the first dose of study drug.

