### 5.2.13 Columbia-Suicide Severity Rating Scale (C-SSRS)

The following outcomes are C-SSRS categories and have binary responses (yes / no). The categories have been re-ordered from the actual scale to facilitate the definition of composite endpoints:

Category 1	Wish to be Dead
Category 2	Non-specific Active Suicidal Thoughts
Category 3	Active Suicidal Ideation with Any Methods (Not Plan) without Intent to Act
Category 4	Active Suicidal Ideation with Some Intent to Act, without Specific Plan
Category 5	Active Suicidal Ideation with Specific Plan and Intent

Category 6	Preparatory Acts or Behavior
Category 7	Aborted Attempt
Category 8	Interrupted Attempt
Category 9	Actual Attempt (non-fatal)
Category 10	Completed Suicide

Suicidal Ideation since baseline – A “yes” answer at any time during double blind treatment to any one of the 5 suicidal ideation questions (categories 1-5) on the C-SSRS.

Suicidal Behavior since baseline – A “yes” answer at any time during double blind treatment to any one of the 5 suicidal behavior questions (categories 6-10) on the C-SSRS.

There will be no imputation of missing data for C-SSRS.

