### 5.13.1 Adverse Events

Treatment-emergent adverse events (TEAEs) are reported according to protocol as any AE that has an onset on or after the dose of study drug or any pre-existing condition that has worsened on or after the first dose of study drug through 14 days following last dose of study drug. The following TEAE flag will be applied to distinguish AEs from TEAEs:

- Any AE that has a start date and time on or after the first dose of study drug and before last dose of study drug + 14 days

A treatment-related AE is defined as an AE as being possibly related or related to the study drug. If an AE has missing relationship it is assumed to be related to the study drug for analysis purposes.

Maximum severity will be assumed for an AE with missing severity.

The following tables will be presented for AEs incidence and/or number of events will be reported as appropriate:

- Overall summary of AEs:
  - TEAEs
  - Treatment-related TEAEs
  - Treatment-emergent serious adverse events (TESAEs)
  - Treatment-related TESAEs
  - TEAEs by severity
  - TEAEs leading to study discontinuation
  - Deaths
- TEAEs by system organ class and preferred term
- Treatment related TEAEs by system organ class and preferred term
- TESAEs by system organ class and preferred term
- TEAEs by system organ class, preferred term and maximum severity
- TEAEs by system organ class, preferred term and strongest relationship
- TEAEs leading to study discontinuation by system organ class and preferred term
- Listing of Serious AEs.
- Listing of Deaths.

Adverse event incidence is counted only once per system organ class and once per preferred term. The number and percent of patients experiencing events are reported. Outputs reported at maximum severity or strongest relationship show the highest severity/relationship reported by a patient per system organ class and preferred term.

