### 5.13.2 Laboratory Data

Descriptive statistics of the observed values and change from baseline (continuous data) will be presented by treatment group and visit for each hematology, urinalysis, chemistry, coagulation, and hormone (ACTH, TSH, cortisol) parameter. Each measurement (continuous data) will be classed as below, within, or above normal range, based on ranges supplied by the laboratory used. Shift tables in relation to the normal range from baseline to each follow-up visit will be presented.

A summary of the number of abnormal parameter values will also be provided. All laboratory data will be listed, with a separate listing only including abnormal (i.e. out of range) values.

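### Post-baseline laboratory, ECG and orthostatic abnormalities first found at an unscheduled assessment are left out of the by-arm abnormality counts, which can therefore be understated

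*SAP*

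**What the plan says.** SAP 5.2.17 sets the general rule: "Only values collected at scheduled assessments values will be tabulated, unless otherwise stated". Values taken at other times are listed: "All repeat/unscheduled assessments will be included in all listings in the relevant appendices".

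The laboratory section (SAP 5.13.2) plans by-visit descriptive statistics and shift tables from baseline to each follow-up visit, and adds: "A summary of the number of abnormal parameter values will also be provided". SAP 5.13.3 counts orthostatic hypotension at each visit. SAP 5.13.4 gives ECG shift tables to each follow-up visit. None of the three says that unscheduled values are used, and none defines an any-time or worst post-baseline category.

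Elsewhere the SAP does look beyond scheduled visits:

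- SAP 5.2.2: "Baseline is defined as the last non-missing value (either scheduled, unscheduled, or repeat) before the patient receives the first dose of study drug".
- SAP 5.2.13, for C-SSRS suicidal ideation since baseline, uses a yes "answer at any time during double blind treatment to any one of the 5 suicidal ideation questions".
- SAP 5.13.1 flags TEAEs by date: "Any AE that has a start date and time on or after the first dose of study drug", up to 14 days after the last dose.

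The Protocol schedules post-baseline laboratory tests, ECGs and vital signs on Days 8, 15, 21 and 28. For the days between visits it says (Protocol 7.2.3, and similarly in the later between-visit sections): "If any assessments are required in order to evaluate an AE, an unscheduled visit may be conducted". For an unexplained noteworthy laboratory value, Protocol 8.2.4 says "the test should be repeated immediately and followed up until it has returned to the normal range" or is explained.

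**The concern.** A test done between visits because a patient is unwell is more likely than a routine one to be abnormal. Under the general rule its result does not enter the tables that count abnormalities by arm. Listings hold it, but a listing gives no count to set three doses against placebo. Safety and tolerability is a secondary objective, so a reader will look to these tables for laboratory, ECG and blood pressure signals by dose.

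**Working it through.** The plan states no abnormality rate, so there is no figure to reproduce. The check traces the rules and then shows how the gap could act.

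**1. Does any stated exception cover these tables?**

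- Baseline (SAP 5.2.2) admits unscheduled and repeat values, but only before the first dose.
- The C-SSRS any-time wording (SAP 5.2.13) applies to that scale alone.
- The TEAE flag (SAP 5.13.1) does not depend on visits, but it counts events, not measured values.
- SAP 5.13.2, 5.13.3 and 5.13.4 contain no exception.

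The general rule therefore governs Table 14.3.4, the haematology, chemistry and ECG shift tables (14.3.7.2, 14.3.7.4, 14.3.7.9) and Table 14.3.6.3.

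**2. How much of the treatment period lies off-schedule?**

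- Days 2 to 28 are 27 days.
- On nominal days, 4 have scheduled assessments and 6 + 6 + 5 + 6 = 23 do not.
- With the ±1-day windows on Days 8, 15 and 21, scheduled assessments can fall on 3 + 3 + 3 + 1 = 10 days, which leaves 27 − 10 = 17.

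These are calendar days, not missed findings. An early-termination visit can also fall on any of them, with laboratory tests, ECG and vital signs (Protocol 7.2.14). SAP 5.2.4 tabulates those values where the mapped visit lacks them.

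**3. Could a short-lived abnormality fall between scheduled days?** Assume that the start day is uniform over Days 2 to 28, and use nominal visit days. The share of start days for which an abnormality of d days overlaps Day 8, 15, 21 or 28 is:

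- d = 1: 4/27 = 15%
- d = 2: 8/27 = 30%
- d = 3: 12/27 = 44%
- d = 5: 20/27 = 74%
- d = 7: 27/27 = 100%

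A finding of a few days can miss every scheduled visit. The tabulation rule matters only if an unscheduled assessment then detects it.

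**4. What would this do to a count?** Let r be the share of patients with an abnormality over all assessments, and u the share of those patients whose abnormality appears only at unscheduled assessments. The scheduled-only rate is r × (1 − u). With r = 10% (assumed):

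- u = 0: 10.0%
- u = 10%: 9.0%
- u = 25%: 7.5%
- u = 50%: 5.0%

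For two arms with assumed rates of 15% and 5% and u = 25% in both, the table shows 15 × 0.75 = 11.25% and 5 × 0.75 = 3.75%. The difference falls from 10 to 7.5 points. The ratio stays at 3, because 11.25/3.75 = 3. The documents give neither r nor u, and u may be zero.

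**5. Do omitted repeats matter?** A repeat under Protocol 8.2.4, or a QTcF confirmation within 15 minutes under Protocol 4.1.1.2, follows an abnormal reading. If that reading was at a scheduled visit, the patient is already counted, and leaving out the repeat does not change the number of patients. Only abnormalities first seen off-schedule are affected.

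**The case against.** The strongest reply is that the AE tables already carry what matters. Protocol 9.1.4 has a new or worsened laboratory abnormality recorded as an AE if it needs treatment or diagnostic tests, leads to discontinuation, has symptoms or is judged clinically significant. Protocol 8.2.2 requires an AE form for noteworthy vital-sign changes, and Protocol 9.2.1 covers isolated laboratory, vital-sign and ECG findings on similar grounds. These events enter TEAE tables by arm, with a relative risk for each dose against placebo. This largely stands. A reader might infer that a dose effect could be absent from every table. The documents do not support that, because findings that meet AE criteria are tabulated whenever they occur.

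The AE route does depend on judgement, which abnormality counts are meant to avoid. In the Phase 1 study summarised in Protocol 14.2.1, QTcF rose by 20 to 46 msec in all volunteers on 200 mg once daily, yet the TEAEs called definitely related include one case of QTcF prolongation.

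A second reply is that a fixed schedule gives every arm the same chance of detection, while unscheduled visits are at the investigator's discretion. For by-visit tables this is right. The shift tables and the orthostatic count are defined by visit, and only the abnormal-laboratory summary is not. What the plan lacks is an any-time summary beside them.

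Third, the use of unscheduled values for Baseline but not afterwards is no flaw in itself. Protocol 10.1 defines Baseline as the last observation before study medication, and a by-visit table needs one value per visit.

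Last, the general rule leaves room for stated exceptions, and the table shells, approved separately under SAP Section 5, are not available here. They might contain one.

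**Conclusion.** The point holds in a narrow form. As the SAP is written, post-baseline laboratory, ECG and orthostatic abnormalities first found at an unscheduled assessment are missing from Table 14.3.4, the laboratory and ECG shift tables and Table 14.3.6.3. An any-time patient count that adds those values can only equal or exceed a count from scheduled values alone, so the omission can understate the number of affected patients. Its size depends on the share of abnormalities seen only off-schedule, which the documents do not give and which may be zero.

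Three stronger readings are tempting and not supported:

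- That the rule keeps every unscheduled value out of the safety tables. Baseline values enter change and shift tables, the C-SSRS derivation is any-time, and TEAEs are flagged by date.
- That 23 of 27 days (or 17, with the windows) measures the loss. It counts days, not findings.
- That the comparison with placebo is shown to be biased toward no difference. With an equal off-schedule share in each arm, absolute differences shrink but ratios do not change. The documents say nothing about unequal shares.

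This is a worthwhile, low-cost improvement to the safety reporting. It does not touch the primary analysis.

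**What to change.** Keep the by-visit summaries on scheduled values. Amend SAP 5.2.17 and 5.13.2 to 5.13.4 so that Table 14.3.4, the laboratory and ECG shift tables and the orthostatic hypotension count each gain a row for any time post-baseline (worst value) over the treatment period, using all scheduled and unscheduled values. Count each patient once per parameter, so that repeats of the same finding do not inflate the row. Add a footnote that patients with more AE work-ups have more chances to show an abnormal value.

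The cost is SAP wording and modest programming, with no new data. The drawback is the unequal ascertainment that the footnote discloses, so the row should be read beside the by-visit tables. The change belongs in an amendment before database lock or, failing that, in the post-lock addendum that SAP Section 5 provides for.

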### **5.2.18 Pooled Study Site**

Sites enrolling fewer than 10 patients might be pooled such that the smallest pooled site becomes the size of the smallest standalone site but not larger than approximately three times the size of the smallest standalone site. The choice of which sites to pool will be done preliminarily once 75% of all patients have been randomized and will be confirmed at the end of the recruitment period and will be based on geographical considerations. The exact pooling strategy will be agreed upon prior to unblinding and database lock and detailed in the CSR.

## **5.3 Conventions**

All data listings, summaries, figures, and statistical analyses will be generated using SAS® version 9.4 or higher.

Summaries will be presented by treatment group or overall. Treatment group labels will be displayed as follows:

LB-102	LB-102	LB-102	Placebo
50 mg	75 mg	100 mg	(N=XX)
(N=XX)	(N=XX)	(N=XX)	

Listings will be sorted in the following order: treatment group, patient, visit, and parameter, unless otherwise stated. All data will be listed, and patients who were not randomized (i.e. screen failures) will be displayed after the randomized treatment groups in relevant listings.

Continuous variables will be summarized by the number of non-missing observations, mean, median, standard deviation (SD), and minimum and maximum. Summaries of PK concentrations will also include geometric means and coefficient of variations (CV), the former being derived as  $\exp(\mu_{ln})$  and the latter as  $\sqrt{\exp(\sigma_{ln}^2) - 1}$  where  $\mu_{ln}$  and  $\sigma_{ln}^2$  are, respectively, the mean and variance calculated on the natural log-transformed concentrations.

Categorical variables will be summarized by presenting the frequency and percent. Percentages will be based either on the number of patients in the column header or on the number of patients in the respective analysis set with available data, as specified in the table footnotes. For each variable, all categories will be shown. Zero frequencies (but not the percent) within a category will be presented.

Means, medians, and percentiles will be displayed to one more decimal place than the data, dispersion statistics (e.g., standard deviation) will have two more decimal places, and the minimum

and maximum will be displayed to the same number of decimal places as reported in the raw data. Percentages will be displayed with one decimal place.

P-values will be quoted to 4 decimal places consistent with SAS PVALUEw.d format set to PVALUE6.4. P-values < 0.0001 will be presented as p<0.0001.

## 5.4 Patient Disposition

Patient disposition will be summarized as follows:

- The number of patients who were screened and who failed screening will be tabulated for the Screened Set alongside the reason for screen failure.
- The number of patients randomized, and who are in each analysis set will be summarized separately for each study site by treatment group and overall.
- The number of study and treatment discontinuations and the reasons for discontinuation will be tabulated by treatment group and overall for all randomized patients.
- The number of patients present at each scheduled visit will be summarized by treatment group for the Safety Analysis Set.

All patient disposition data will be listed.

## 5.5 Protocol Deviations

PDs will be summarized by classification (minor, major) and reason. A listing of PDs will be provided within Appendix 16.2 of the CSR.

## 5.6 Baseline Comparability

The comparability of treatment groups with respect to patient demographics and baseline characteristics will be assessed in a descriptive manner.

Standard continuous or categorical variable summaries will be presented for the Safety Analysis Set by actual treatment group for the following variables:

- Demographics
  - Age at Informed Consent (years),
  - Gender, n (%) ('Male', 'Female'),
  - Fertility status for women, n (%) (a) ('Childbearing Potential', 'Post-menopausal', 'Surgically Sterile'),
  - Ethnicity, n (%) ('Hispanic or Latino', 'Not Hispanic or Latino'),
  - Race, n (%) ('American Indian or Alaska Native', 'Asian', 'Black or African American', 'Native Hawaiian or Other Pacific Islander', 'White', 'Multiple Race', 'Unknown', 'Not Reported').
- Other baseline characteristics

- Weight (kg),
- Height (cm),
- Body Mass Index (kg/m^2),
- Waist Circumference (cm).

The MINI 7.0.2 questionnaire with the Borderline Personality Disorder (BPD) module will only be listed.

## **5.7 Medical History**

Separate tabulations of previous and ongoing conditions at screening will be presented by actual treatment group and overall for the Safety Analysis Set. Conditions will be presented by Medical Dictionary of Regulated Activities (MedDRA) primary system organ class and preferred term, using version 26.1 or higher for coding.

All medical history information will also be listed.

## **5.8 Prior and Concomitant Medications**

Prior medications are defined as all medications that were stopped in the 30 days before ICF sign-off, whereas concomitant medications are defined as medications taken on or after such date.

Separate tabulations will be produced for prior and concomitant medications presented by actual treatment group and overall for the Safety Analysis Set. Concomitant medications will be coded using the WHO dictionary (version B3 Global Mar-2023 or later) and summarized using Anatomic Therapeutic Chemical (ATC) Level 2.

Prior medication washout information will also be listed separately.

